2.2.4. Study Drug

Study drug consists of NEOD001 or placebo. The NEOD001 dose is 24 mg/kg (not to exceed 2500 mg). Each vial of 500 mg of NEOD001 will be reconstituted with 9.6 mL sterile water for injection to a concentration of 50 mg/mL, resulting in a buffered, isotonic, preservative-free solution with a total extractable volume of 10 mL. Study drug will be prepared in a 250 mL IV bag of 0.9% saline. The equivalent volume of reconstituted NEOD001 will be withdrawn from the IV bag prior to transferring the drug solution into the IV bag, such that the total IV bag volume will be 250 mL. A separate placebo will not be provided for this study. Subjects who are assigned to the placebo group will be administered a 250 mL IV bag of 0.9% saline, which will look identical to the NEOD001 infusion bag. The volume contained in the administration tubing

should be completely flushed using approximately 30 mL of 0.9% Sodium Chloride Injection after administration of study drug.

Please refer to the protocol for complete product details.

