- For missing stop day and month – Day and month will be imputed as the last day of the year (i.e., 31 December).
- Imputed stop dates must be on or after the start date.

If a time required for calculation related to exposure is missing, the following standards will be applied:

- If start time is missing for an infusion where the volume recorded on the eCRF is greater than 0 mL then start time will be imputed as the pre-dose time of vital signs at the same visit + 1 minute. This should only be done for the first dose time within a given visit should there be more than one record.
- If stop time is missing for an infusion where the volume is greater than 0 mL then stop time will be imputed as the ‘immediately after infusion’ time of the vital signs at the same visit - 1 minute. This will only be done for the last dose time within a given visit should there be more than one record.
- If vital sign assessment times are not available, infusion start date/time is missing, and infusion stop date/time is non-missing then the start date/time will be imputed as stop date/time - 2 hours at the Month 1 Day 1 visit or as the stop date/time - 1 hour for all other visits

If vital sign assessment times are not available, infusion stop date/time is missing, and infusion start date/time is non-missing then the stop date/time will be imputed as start date/time + 2 hours at the Month 1 Day 1 visit or as the start date/time + 1 hour for all other visits. All data recorded on the case report form will be included in data listings that will accompany the CSR.

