9.1. Extent of Exposure

The total patient exposure years (PEY) for each subject is defined as the time interval between the first dose and the last dose, inclusive, of study drug based on the subject's study drug administration information. One PEY is the equivalent of 1 subject exposed to study drug for 1 year. Two subjects who are exposed to study drug for half a year together contribute one PEY. The total PEY of a treatment group is the sum of the person exposure years of each subject in that treatment group. Duration of exposure is defined in days as the date of the last infusion of study drug – the date of the first infusion of study drug + 1.

Study drug exposure will be summarized by treatment group and will include:

- The number of subjects exposed to NEOD001, the total PEY, and duration of exposure will be summarized using descriptive statistics. This summary will be repeated for all general and special baseline subgroups defined in Section 6.
- Total Number of Infusions received will be determined for each subject by number of times the start time of drug infused is reported. If multiple infusion start times are reported on a single day, then only 1 infusion will be counted for that day. If the start time of drug infused is missing but total volume infused is greater than 0 mL, 1 infusion will be counted for that day.
- Percentage of Expected Infusions will be determined for each subject as the total number of infusions received divided by the total number of expected infusions multiplied by 100. Total number of expected infusions will be defined as the maximum of (the total number of infusions received, and the floor of ((EOS/ETD date - first infusion date + 1)/28), i.e. integer part of the function).
- Total Number of Dose Interruptions will be determined for each subject by the number of times the IV was not completed.

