- Dose Strength (mg/kg) will be calculated for each subject for each visit. Total dose (mg) per infusion is not captured on the eCRF. Total dose (mg) is captured in the materials kit schedule maintained by IWRS. After unblinding, the total dose in mg will be calculated as the number of NEOD001 vials infused at each visit per IWRS, multiplied by 500 mg per vial. Total dose (mg) will be divided by the weight used to calculate total dose. If the total dose (mg) is missing but the total duration of infusion is 120 +/- 10 minutes for Month 1-Day 1 or the total duration of infusion is 60 +/-10 minutes for visits after Month 1-Day1 and IV completed is marked "Yes" then total dose will be imputed to be equal to the planned dose strength (described below). Dose strength will only be calculated where both the total dose and weight used are available. Once visit/individual specific Dose Strengths are determined, subjects will be assigned a single average Dose Strength value across all visits to be used for summary statistics in the table.

- Percent of Planned Dose Strength will be determined by dividing the actual dose strength by the planned dose strength. Calculation of actual dose strength is described above. Planned dose strength will be determined in a similar manner except the planned dose will be calculated by multiplying the reported NEOD001 dose concentration by the weight used.
- Total Number of Dose Reductions will be determined for each subject by the number of times the percent of planned dose was less than 100.

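### SAP 9.1 builds the planned dose on an undefined term and leaves out the 2500 mg maximum, so the dose-reduction count depends on how it is programmed; the missing-dose unit, the 9.4 mBMI formula and a 9.3 laboratory limit are also misstated

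*SAP*

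**What the plan says.** SAP 9.1 defines the exposure variables as follows.

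- **Actual dose.** The section states "Total dose (mg) is captured in the materials kit schedule maintained by IWRS", but then derives the figure from a vial count: "total dose in mg will be calculated as the number of NEOD001 vials infused at each visit per IWRS, multiplied by 500 mg per vial". Dividing by the weight used gives dose strength in mg/kg.
- **Planned dose.** "the planned dose will be calculated by multiplying the reported NEOD001 dose concentration by the weight used". The SAP does not define the dose concentration. For the drug product, SAP 2.2.4 uses the word concentration only for the reconstituted vial (50 mg/mL).
- **Dose reductions.** Counted "by the number of times the percent of planned dose was less than 100", with no tolerance.
- **Missing total dose.** If the infusion was completed in the expected time, "total dose will be imputed to be equal to the planned dose strength".
- **Dose interruptions.** Counted separately, "by the number of times the IV was not completed".

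SAP 2.2.4 does give the maximum: "The NEOD001 dose is 24 mg/kg (not to exceed 2500 mg". Protocol 5.3 gives it too and places the threshold at 104.2 kg. The planned-dose rule in 9.1 does not mention it.

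Two nearby definitions conflict with other text. SAP 7.2 defines mBMI as weight divided by height squared, times albumin. SAP 9.4 has weight times height squared, divided by albumin, under the same printed unit. SAP 9.3 gives the fallback lower limit for creatinine clearance as 90 mL/sec, equated to 1.5 mL/min. SAP section 10, which lists changes from the protocol, mentions none of these points.

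**The concern.** Protocol 8.2 requires exposure summaries that include dose reductions and dose strength. Under 9.1 these tables turn on a term that each programmer must interpret. One reading turns protocol-compliant capped infusions into reductions; the other compares a reduced dose with itself. The imputation sentence puts a mg/kg figure into a mg variable. The two mBMI formulas would give a baseline table and a safety table on different scales. At stake is whether the descriptive account of how much drug was given, and how often it was reduced, can be read at face value.

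**Working it through.** **Inputs.** Dose 24 mg/kg, maximum 2500 mg, cap weight 104.2 kg (protocol 5.3); 500 mg per vial (protocol 5.1.1, SAP 9.1); up to 12 infusions (protocol 5.3). The documents give no body weights, so those below are illustrations.

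**The plan's own figure.** 2500 / 24 = 104.17, which rounds to 104.2 kg. It reproduces.

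**Reading A: the term means 24 mg/kg.** Percent of planned = 2500 / (24 × weight) for a full capped infusion.

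| Weight (kg) | Planned without cap (mg) | Full dose (mg) | Percent of planned | Counted as reduction |
|---|---|---|---|---|
| 104.2 | 2500.8 | 2500 | 99.97 | yes |
| 110 | 2640 | 2500 | 94.7 | yes |
| 120 | 2880 | 2500 | 86.8 | yes |

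Each full infusion is counted, so one such subject could contribute up to 12 false reductions. With the cap in the denominator, every row is 2500 / 2500 = 100%.

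**Reading B: the term means the mg/kg level given at that visit.** At 110 kg the level is 2500 / 110 = 22.7 mg/kg, planned dose is 2500 mg, and the score is 100%. A real 50% reduction, however, is also compared with itself. The protocol describes that reduction in two ways: 5.4.2 prints 12.5 mg/kg, while half of the 24 mg/kg in 5.3 is 12 mg/kg. At 70 kg:

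| Basis of the halved dose | mg | Score from mg records | Score from whole vials (2 vials = 1000 mg) |
|---|---|---|---|
| 12 mg/kg | 840 | 840/840 = 100% | 1000/840 = 119% |
| 12.5 mg/kg | 875 | 875/875 = 100% | 1000/875 = 114% |

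On either figure the reduction is not counted.

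**Vial counting.** This matters only if IWRS holds whole vials, which the documents do not settle. A full dose at 70 kg is then 4 vials: 2000 / 1680 = 119% of planned. At 80 kg it is 2000 / 1920 = 104%.

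**Imputation unit.** The variable to be filled is in mg; the filler is in mg/kg. Taken literally at 70 kg, 24 / 70 = 0.34 mg/kg, or 1.4% of planned. One such visit in 12 would lower a 24 mg/kg average to (11 × 24 + 0.34) / 12 = 22.0 mg/kg.

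**mBMI.** For 70 kg, 1.70 m and albumin 35 g/L (illustrative):

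- 7.2: 70 / 1.70² × 35 = 848
- 9.4: 70 × 1.70² / 35 = 5.8

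As albumin goes from 25 to 45 g/L, the 7.2 value rises from 605.5 to 1090.0 and the 9.4 value falls from 8.09 to 4.50. The direction reverses. The printed unit (kg/m² times g/L) fits only 7.2.

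**Laboratory limit.** 90 mL/min / 60 = 1.5 mL/sec. As printed, 90 mL/sec would be 90 × 60 = 5400 mL/min.

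**How many subjects could reach the cap.** This is an assumption. With weights normal, truncated to 40–150 kg, mean 70 to 80 kg and SD 12 to 15 kg, between 0.2% and 5.4% exceed 104.17 kg. Of about 65 NEOD001 subjects (half of about 130), that is 0.1 to 3.5.

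**The case against.** The best defence is that these are wording slips in descriptive tables and that competent programming would resolve them. Much of that stands.

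- **Real reductions would not vanish from the report.** A reader might infer this from Reading B, but the documents do not support it. Protocol 5.4.2 and 5.4.3 tie reductions to adverse events. Such events should appear in the table of events leading to dose reduction (SAP 9.2, which uses its own action-taken field), protocol 5.5 has the eCRF record why treatment was adjusted, and SAP 9.1.1 flags modified doses in a listing. Only this one count would miss them.
- **The 1.4% imputation result is unlikely in practice.** It needs a dimensional error to survive quality control, and nothing suggests that total doses will be missing. What stands is the unit mismatch in the sentence.
- **A general overstatement of dose strength is not shown.** Vials times 500 mg invites that inference, but it holds only if IWRS records whole vials.
- **The term may be clear in a specification we do not have.** The word reported suggests a data field, and only mg/kg works dimensionally. The documents still do not say whether the field is the protocol level or the visit level, or whether it is already capped, and that decides which error occurs.
- **The mBMI and laboratory-limit errors are typographical.** The unit in 9.4 reveals the intended formula. The limit applies only where the central laboratory supplies none, and no effect on shift tables follows: SAP 9.3.4 restricts low/normal/high shifts to tests without CTCAE grades, and the documents do not say creatinine clearance is one.

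**Conclusion.** The derivation rules are wrong or incomplete as written and should be corrected before the exposure tables are programmed. Under the 24 mg/kg reading, full capped infusions are counted as reductions (94.7% at 110 kg, 86.8% at 120 kg); under the visit-level reading, real halvings score about 100% and leave this count. The mg/kg imputation, the inverted mBMI formula and the swapped units are errors on the face of the text.

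The reach is limited. SAP section 9 makes safety tables descriptive unless otherwise specified. Efficacy tests, exposure years, infusion counts and adverse-event incidence do not use these variables, so a reader should not infer any threat to the trial's conclusions. The false-reduction branch also needs subjects at or above 104.2 kg; their number is unknown and may be zero. The remaining points do not depend on weight. Confidence is medium, because the meaning of the undefined term may be fixed in eCRF or IWRS specifications outside the documents.

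**What to change.** 1. Define planned dose in mg by the documents' existing rule: the smaller of 24 mg/kg × weight used and 2500 mg. Name the data source of each input.
2. Count a reduction only when the mg prepared for the visit falls below that capped planned dose by more than a stated rounding tolerance. If only vial counts exist, count one when fewer vials are recorded than the capped dose needs. A full capped infusion is then never flagged, and a 50% reduction is detected at every weight from 41.7 to 160 kg on both printed figures.
3. Report incomplete infusions separately, as the interruption count already does.
4. Impute a missing total dose with planned mg.
5. State what IWRS holds. If only vial counts, label the result as vials dispensed. The eCRF records infused volume (SAP 4.3 refers to "an infusion where the volume recorded on the eCRF is greater than 0 mL"). If it is used to scale mg, divide by the total volume actually prepared for that visit and exclude the flush. A fixed 250 mL would not do, since protocol 5.3 allows the dose to be split across bags and requires a flush of about 30 mL.
6. Use the 7.2 mBMI formula in 9.4, and give the fallback limit as 90 mL/min = 1.5 mL/sec.
7. Reconcile protocol 5.4.2 (12.5 mg/kg as a 50% reduction), 5.3 (24 mg/kg) and 5.4.3 (50%, no figure) before reductions are classified. This review takes no view on which is right.

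The cost of items 1 to 6 is SAP wording and derivation code. No new data are needed unless actual mg is taken from IWRS or pharmacy records, and nothing changes for subjects. Item 7 is for the sponsor to settle in the protocol.

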9.1.1. Use of Premedication

The use of premedications will be summarized for any infusion and by each planned infusion by treatment group and will include the following:

- Total Number of Subjects Infused
- Total Number of Infusions Administered: number of times the start time of drug infused is reported. If multiple infusion start times are reported on a single day, then only 1 infusion will be counted for that day. If the start time of drug infused is missing but total volume infused is greater than 0 mL, 1 infusion will be counted for that day.
- Number of Subjects Receiving Premedication
- For subjects receiving premedication, number of infusions requiring premedication per subject: note that because this value is by definition 1 for by-infusion summaries, this should only be presented for the any-infusion summary.
- For subjects requiring premedication, number of premedications per subject per infusion.

All recorded and derived exposure data will be presented in a by-subject data listing and any dose modifications will be flagged.

9.2. Adverse Events

Verbatim terms on eCRFs will be mapped to PTs and SOCs using MedDRA version 19.0. AEs will be reported and severity will be categorized using the Common Terminology Criteria for Adverse Events (CTCAE, Version 4.03).

Pretreatment AEs are those AEs with a start date prior to the first infusion of study drug. All AE summaries will be restricted to TEAEs, which are defined as any AE that newly appears, increases in frequency, or worsens in severity following initiation of study drug and through the last study visit or up to 30 days after date of last dose, whichever is later. If it cannot be determined whether the AE is treatment emergent due to a partial onset date, then it will be counted as such.

Each AE summary will be displayed by treatment group. Summaries that are displayed by SOC and PT will be ordered by descending order of NEOD001 incidence of SOC and PT within each SOC. Summaries of the following types will be presented:

- Overall summary of AEs including the number and percent of subjects with at least one of the following:
 - Any TEAE

- TEAE by maximum CTCAE Grade
- CTCAE Grade ≥ 3 TEAE
- Serious TEAE
- TEAE leading to death (outcome="Fatal" or severity=CTCAE grade 5)
- Treatment-related TEAE
- Treatment-related serious TEAE
- Treatment-related TEAE of CTCAE \geq Grade 3
- Treatment-related TEAE leading to death
- TEAE leading to infusion interruption
- TEAE leading to dose reduction of study treatment
- TEAE leading to dose being held
- TEAE leading to prolongation of infusion time (>2.5 hours)
- Infusion associated TEAE overall
 - Infusion associated TEAE with premedication concomitant medication for infusion related reaction
 - Infusion associated TEAE without premedication concomitant medication for infusion related reaction
- TEAE leading to study drug withdrawal
- Subject incidence of TEAEs by MedDRA SOC and PT. This summary will be repeated for all general and special baseline population subgroups defined in Section 6.
- Subject incidence of TEAEs by MedDRA SOC and PT occurring in $\geq 5\%$ of NEOD001 subjects with greater frequency than placebo.
- Subject incidence of TEAEs by MedDRA SOC and PT occurring in $\geq 10\%$ of NEOD001 subjects with greater frequency than placebo.
- Subject incidence of TEAEs by MedDRA SOC and PT occurring with greater frequency than placebo.
- Subject incidence of TEAEs by MedDRA SOC and PT occurring in NEOD001 subjects at frequencies of Very common ($\geq 10\%$); Common (≥ 1 to $< 10\%$); Uncommon (≥ 0.01 to $< 1\%$); Rare (≥ 0.001 to $< 0.01\%$); Very rare ($< 0.001\%$).
- Subject incidence of TEAEs by MedDRA SOC, PT, and highest severity (CTCAE grade). At each level of subject summarization, a subject is classified according to the highest severity if the subject reported 1 or more events. AEs with missing severity (CTCAE grade) will be considered grade 3 (severe) for this summary.
- Subject incidence of CTCAE grade 3 or higher TEAEs by MedDRA SOC and PT. At each level of subject summarization, a subject is classified according to the highest severity if the subject reported 1 or more events. AEs with missing severity (CTCAE

grade) will be considered grade 3 (severe) for this summary. This summary will be repeated for the general and special baseline population subgroups defined in Section 6.

- Subject incidence of TEAEs by MedDRA SOC, PT, and closest relationship to study drug (Related/Not Related). At each level of subject summarization, a subject is classified according to the closest relationship to study drug if the subject reported 1 or more events. AEs with a missing relationship will be considered related for this summary.
- Subject incidence of related TEAEs by MedDRA SOC and PT. At each level of subject summarization, a subject is classified according to the closest relationship to study drug if the subject reported 1 or more events. AEs with a missing relationship will be considered related for this summary.
- Subject incidence of related CTCAE grade 3 or higher TEAEs by MedDRA SOC and PT. At each level of subject summarization, a subject is classified according to the highest severity if the subject reported 1 or more events. AEs with missing severity (CTCAE grade) will be considered grade 3 (severe) for this summary. AEs with a missing relationship will be considered related for this summary.
- Subject incidence of serious TEAEs by MedDRA SOC and PT. This summary will be repeated for all general and special baseline population subgroups defined in Section 6.
- Subject incidence of serious related TEAEs by MedDRA SOC and PT. At each level of subject summarization, a subject is classified according to the closest relationship to study drug if the subject reported 1 or more events. AEs with a missing relationship will be considered related for this summary.
- Subject incidence of TEAEs leading to study drug withdrawal by MedDRA SOC and PT. This is a subset of the AEs where Action Taken with Study Treatment is checked as “Drug Permanently Withdrawn” is checked.
- Subject incidence of TEAEs leading to infusion interruption by MedDRA SOC and PT. This is a subset of the AEs where Action Taken with Study Treatment is checked as “Dose Interrupted” is checked.
- Subject incidence of TEAEs leading to dose reduction by MedDRA SOC and PT. This is a subset of the AEs where Action Taken with Study Treatment is checked as “Dose Reduced” is checked.
- Subject incidence of TEAEs leading to dose held by MedDRA SOC and PT. This is a subset of the AEs where Action Taken with Study Treatment is checked as “Dose Held” is checked.
- Subject incidence of TEAEs leading to prolongation of infusion time (>2.5 hours) by MedDRA SOC and PT.

All of the above tables will be repeated only for MedDRA PT, excluding MedDRA SOC.

The following listings will be presented by treatment group and subject:

- All AEs
- SAEs (this is a subset of the AEs where serious is marked as “Yes”)

- CTCAE Grade 3 or higher AEs (this is a subset of AEs where severity is marked as CTCAE grade 3, 4, or 5)
- Related AEs (this is a subset of the AEs where relationship marked as “Related”)
- AEs leading to Study Drug Withdrawal (this is a subset of the AEs where Action Taken with Study Treatment is checked as “Drug Permanently Withdrawn”)
- AEs leading to death (This is a subset of the AEs where outcome is indicated as “Fatal” or the CTCAE grade is 5)
- AEs resulting in any dose change (i.e. interruption, reduction, held, or prolongation)
- All adverse events for subjects who received the wrong study drug

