3 STUDY PLAN

3.1 Study Design

This is a global, multicenter, Phase 2b, randomized, double-blind, placebo-controlled, two-arm, parallel-group efficacy and safety study of NEOD001 as a single agent administered intravenously in adults with AL amyloidosis who had a hematologic response ([Appendix 1](#)) to previous treatment for their amyloidosis (e.g., chemotherapy, ASCT) and have persistent cardiac dysfunction.

Subject screening will occur during the 28 days prior to the first administration of study drug (i.e., Month 1-Day 1 Visit). If all eligibility requirements are met, the subject will be enrolled and Screening assessments will be completed. Screening assessments are listed in [Table 1](#).

Study visits will occur every 28 days based on scheduling from Month 1-Day 1. A ± 5 -day window is allowed for visits starting after Month 1. Subjects may receive up to 12 infusions of study drug. Subjects who discontinue study drug before the End of Study (EOS) Visit should have an Early Treatment Discontinuation (ETD) Visit 30 (± 5) days after their final administration of study drug (per [Section 6.2](#)). If willing, subjects may continue in the study and have monthly assessments, through Month 12, per [Appendix 13](#). Subjects who complete the study and meet the eligibility criteria will be considered for entry into a separate open-label extension study, during which subjects will receive active treatment and may receive concurrent chemotherapy.

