4.3 Early Treatment Discontinuation

If the subject discontinues study drug prior to the EOS Visit, they should return for an ETD Visit 30 (\pm 5) days after their final administration of study drug as per [Section 6.2](#). If a subject fails to return for the scheduled visit, a documented effort must be made to determine the reason. If the subject cannot be reached by telephone after 2 attempts, a certified letter will be sent to the subject (or the subject's legally authorized representative, if appropriate) requesting contact with the Investigator. This information will be recorded in the study records.

If the subject discontinues study drug prior to the EOS, but is willing to continue to participate in study visits, the subject should have an ETD Visit 30 (\pm 5) days after his/her final administration of study drug (per [Section 6.2](#)) and then have assessments monthly, through Month 12 per [Appendix 13](#). The subject will not have an EOS Visit. The most important visit is the Month 12-Day 1 Visit, so if a subject is unwilling to continue monthly visits, every effort should be made for the subject to return to the clinic and complete the Month 12-Day 1 Visit on schedule. All visits after the ETD Visit should occur on schedule, that is, at the time when their visit would have occurred had they remained on study drug. Following the Month 12-Day 1 Visit, subjects will be followed for vital status per [Section 6.4](#).

Reasons for early discontinuation from study drug treatment may include, but are not limited to:

- Hematologic progression and initiation of chemotherapy is required; chemotherapy regimen should be documented on the appropriate electronic case report form (eCRF).
- Need for organ transplant or major surgery.
- A suspected NEOD001-related immunologic reaction – collect additional serum samples, if possible, during the period following the treatment stoppage to allow for the determination of the persistence of anti-NEOD001 antibodies. At a minimum, samples should be collected at the ETD Visit and 3 months after the ETD Visit, if the subject agrees to return to the clinic.
- Occurrence of an AE or clinically significant laboratory abnormality that, in the opinion of the Investigator, warrants the subject's permanent discontinuation from study drug treatment; the Medical Monitor should be notified as soon as possible of any discontinuation of study drug due to an AE.

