7 ADVERSE EVENTS/SERIOUS ADVERSE EVENTS AND REPORTING

7.1 Adverse Events—Definition

An AE is any untoward medical occurrence associated with the use of a drug in humans, whether or not considered drug related. An AE can, therefore, be any unfavorable and unintended sign (including a laboratory finding, for example), symptom, syndrome, or disease temporally associated with the use of a medicinal product, whether or not considered related to the medicinal product. Examples include:

- Any treatment-emergent signs and symptoms (events that are marked by a change from the subject's baseline/entry status [e.g., an increase in severity or frequency of preexisting abnormality or disorder])
- All reactions from study drug, abuse of drug, withdrawal phenomena, sensitivity, or toxicity to study drug
- Apparently unrelated illnesses
- Injury or accidents
- Exacerbations of the underlying disease (indication)
- Extensions or exacerbations or symptomatology, subjective events reported by the subject, new clinically significant abnormalities in clinical laboratory, physiological testing, or physical examination

The reporting period for AEs is from the time that the ICF is signed through the last study visit or through 30 days after the last dose of study drug, whichever is later. All AEs, whether or not related to the study drug, must be fully and completely documented on the eCRF and in the subject's medical notes. The following attributes must be assigned: description, dates of onset and resolution, severity, assessment of relatedness to study drug (either related or not related), and action taken. The Investigator may be asked to provide additional follow-up information.

In the event that a subject is withdrawn from the study because of an AE, it must be recorded on the eCRF. The subject should be followed and treated by the Investigator until the AE has resolved, stabilized, or a new chronic baseline has been established.

The Investigator must report all AEs. At each visit the Investigator will ask the subject a nonspecific question (e.g., "Have you noticed anything different since your last visit?") to assess whether any AEs have been experienced since the last report or visit. Adverse events will be identified and documented on the eCRF in appropriate medical terminology. The severity and the relationship to the study drug will be determined and reported on the eCRF ([Sections 7.2 and 7.3](#)).

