8.4 Analysis of Safety Endpoints

Safety will be assessed through summaries of AEs, changes in laboratory test results, and changes in vital signs. Additional safety assessments include 12-lead ECGs. Safety data will be summarized by treatment group using the Safety Population.

All collected AE data will be listed by study site, subject number, and visit. All AEs occurring on or after treatment on Day 1 will be summarized. TEAEs are defined as AEs or SAEs that occur from the initiation of the first study drug infusion through the 30-day period following the last dose of study drug. In addition, all SAEs, including deaths, will be listed and summarized separately.

Descriptive statistics of the quantitative laboratory results, vital signs, and ECG parameters will be presented by treatment group and study visit, as well as the change from baseline at each visit. The baseline value is defined as the last non-missing value before the initial administration of study drug.

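### The SAP ends the treatment-emergent AE window later than the protocol does, without listing the change, and plans no AE table cut at the protocol's window

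*SAP*

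**What the plan says.** Protocol Section 8.4 defines TEAEs as events that "occur from the initiation of the first study drug infusion through the 30-day period following the last dose of study drug". SAP Section 9.2 instead runs the window "through the last study visit or up to 30 days after date of last dose, whichever is later". The same SAP section states that "All AE summaries will be restricted to TEAEs", so this definition governs the general, Grade 3 or higher, serious, fatal, related and subgroup tables.

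Three other parts of the protocol bear on the point:

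- **Collection period.** Section 7.1 collects AEs "through the last study visit or through 30 days after the last dose of study drug, whichever is later". This is the end point that the SAP uses, but in the protocol it is a rule for collection, not the TEAE definition.
- **General summary.** The sentence in Section 8.4 just before the TEAE definition says "All AEs occurring on or after treatment on Day 1 will be summarized".
- **Visits off drug.** Section 3.1 provides that "If willing, subjects may continue in the study and have monthly assessments, through Month 12". Section 4.3 repeats this and gives hematologic progression needing chemotherapy as a reason for stopping. Appendix 13 schedules an AE assessment at each of these visits.

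SAP Section 10 lists changes from the protocol's analyses, including one to the Safety Population. The TEAE window is not among them.

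**The concern.** Under the SAP wording, a subject who stops drug early and stays for monthly visits goes on generating treatment-emergent events for as long as visits continue. Chemotherapy is prohibited as concomitant treatment (Protocol Section 5.6.2), but a subject may stop study drug in order to start it. Toxicity of that chemotherapy, months after the last infusion, would then appear in the TEAE tables of a single-agent study.

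Two things are at stake. The tables would carry the label TEAE without meeting the protocol's definition, and a reader who relies on Section 10 would not know it. And because every AE summary is restricted to the SAP's set, no table would show events within the protocol's window alone.

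**Working it through.** There is no stated figure to reproduce; the check compares two end dates.

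**Inputs**

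- Visits every 28 days from Month 1-Day 1 (Protocol Sections 3.1 and 6.1.2), so infusion k falls on Day 1 + 28 × (k − 1).
- Month 12-Day 1 falls on Day 1 + 28 × 11 = Day 309. SAP Table 3 has a target of 308, a one-day difference in numbering. With the ±5-day visit window this is Day 304 to 314.
- After discontinuation, visits stay on the original schedule through Month 12-Day 1 and there is no EOS visit (Protocol Section 4.3, Appendix 13).
- For completers the EOS visit is 30 (±5) days after the last dose (Protocol Section 6.2).

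**Formulas**

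- Protocol window ends on: day of last dose + 30.
- SAP window ends on: the later of (day of last dose + 30) and the last study visit.
- Extra days = SAP end − protocol end.

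**Results**, assuming the early discontinuer attends through Month 12-Day 1:

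| Last infusion | Day of last dose | Protocol end | SAP end (range) | Extra days (range) | Extra months (÷ 30.4375) |
|---|---|---|---|---|---|
| Month 1 | 1 | 31 | 309 (304–314) | 278 (273–283) | 9.1 |
| Month 3 | 57 | 87 | 309 (304–314) | 222 (217–227) | 7.3 |
| Month 6 | 141 | 171 | 309 (304–314) | 138 (133–143) | 4.5 |
| Month 9 | 225 | 255 | 309 (304–314) | 54 (49–59) | 1.8 |
| Month 10 | 253 | 283 | 309 (304–314) | 26 (21–31) | 0.9 |
| Month 12 (completer) | 309 | 339 | 339 (339–344) | 0 (0–5) | 0 to 0.2 |

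A discontinuer whose last visit is the ETD visit, 30 (±5) days after the last dose, is in the same position as a completer: at most 5 extra days.

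**What cannot be computed.** The effect on a TEAE percentage would need the number of early discontinuers who keep attending, how many start chemotherapy, their event rates off drug, and the split by arm. The documents give none of these.

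**The case against.** The best defence is the general-summary sentence in Protocol Section 8.4, taken with the collection period in Section 7.1. The protocol already requires late off-drug events to be collected and summarized, so the SAP does not bring in events that the protocol meant to keep out of every table. That stands, and it narrows the point to labelling, disclosure and the missing summary. It does not make the two TEAE definitions agree: the protocol states collection, general summary and TEAE separately, and only the TEAE definition ends "through the 30-day period following the last dose of study drug".

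A reader might infer that the wider window biases the comparison between arms. The documents do not support this. No imbalance in discontinuation or retention is given, and a window closing 30 days after the last dose also gives unequal follow-up if one arm stops earlier. On-treatment and on-study summaries each have a known weakness. Nor can the wider window be called conservative, since off-drug events may dilute a real difference as easily as create one.

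A reader might also infer that TEAE follow-up becomes about five times as long. That holds only for a near-worst case: a subject who stops after infusion 2 (Day 29, protocol end Day 59) and attends to Day 309, where 309/59 = 5.2. Attendance after the ETD visit is voluntary.

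The SAP has some mitigation. Infusion-associated events and events within 24 hours of an infusion have their own summaries (Section 9.2.1), and listings carry relative study day. Related events are tabulated separately, but on the same wide window and with a missing relationship counted as related. SAP Section 9.1 counts exposure only from first to last dose, but the Section 9.2 tables are subject incidences, so that mismatch does not distort a planned output.

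**Conclusion.** The two definitions conflict in current text, the change is not listed in SAP Section 10, and no planned AE table uses the protocol's cut-off. For early discontinuers who keep attending, up to about 278 off-drug days (range 273 to 283) are labelled treatment-emergent, falling to about 138 for a last infusion at Month 6. For completers it is at most about 5 days. These figures assume visits on the 28-day schedule and attendance through Month 12-Day 1.

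Chemotherapy-era events are a possible part of the added time, of unknown size. Some could fall inside the protocol's 30 days as well; the SAP wording extends their inclusion to the last visit. Distortion of AE rates or of the comparison between arms is not shown and cannot be computed from the documents. The point should be settled before database lock as a matter of definition and disclosure.

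**What to change.** In SAP Section 9.2, use the protocol window (first infusion through 30 days after the last dose) for the TEAE tables. Add one table, by arm, of AEs starting after that window, flagging those that start after chemotherapy begins. The protocol's statement that all AEs from Day 1 are summarized is then still met. The data should already exist: AEs and concomitant therapy are recorded at the post-discontinuation visits, and the chemotherapy regimen is to be documented on the eCRF.

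If the sponsor prefers the wider window, list and justify it in Section 10, and add an overall, a serious and a Grade 3 or higher AE summary limited to last dose plus 30 days.

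The cost is SAP wording and one or a few extra tables.
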